A more relevant drug to the question of chronic pain after surgery is gabapentin, and some clinical trials have suggested that perioperative treatment of this drug can reduce the incidence of this problem (Schmidt, 2013). In the NIH application we propose to test gabapentin rather than modafinil because our previous work with direct measures in rats and cerebrospinal fluid norepinephrine sampling in humans is consistent with gabapentin activating LC in both species (Hayashida, 2007). The pupil measurements in this feasibility study will more directly assess whether gabapentin does indeed increase LC activity in humans. Should it fail to demonstrate a reasonable effect size to dilate the pupil, we will revise the NIH application to study modafinil rather than gabapentin. As such, these preliminary data are very important to the design of the final study.

Study Design.

Hypotheses: (1) Gabapentin and modafinil will increase resting pupil diameter with a moderate effect size in patients with osteoarthritis; (2) Expectations will modify pain experience with a moderate effect size in these patients

Study design: Single-center, randomized, controlled study of gabapentin, modafinil, and placebo in 30 subjects (10 per group) with moderate osteoarthritis pain of the hip or knee or healthy individuals without pain

Primary outcome measures: (1) Resting pupil diameter and response to noxious stimuli after study drug; (2) Interaction between resting pupil diameter and correlation of cognitive-affective state to pain reporting.

Inclusion criteria: Adult, nonpregnant adults scheduled with moderate pain (verbal score of $\geq 4 \leq 7$ on 0-10 scale for average pain intensity with normal activity) from osteoarthritis of the knee or hip, or healthy individuals without pain, American Society of Anesthesiologists physical status 1-3, able and willing to perform the study procedures, including sitting in a chair for 45 min. Individuals must be able to read.

Exclusion criteria. (1) Inability to complete questionnaires; (2) Pregnancy; (3) Currently taking gabapentin or > 50 mg morphine equivalents/day; (4) advanced or unstable cardiac, pulmonary, renal or hepatic dysfunction; (5) history of previous eye surgery; (6) psychotic disorder or a recent psychiatric hospitalization.

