Data analysis. Pupil diameter data will be conditioned to remove blink and saccade artifacts and smoothed using an autoregressive filter. The local resting diameter will be determined representing the average smoothed value for the 500 msec preceding the stimulus onset. The pupil response to each stimulus is calculated as the mean pupil diameter during the 5 sec stimulus after accounting for lag time from onset of stimulus to onset of pupil response and is expressed as a % change from the local resting diameter (see our preliminary data for examples). Multidimensional Scaling (MDS) will be used to create a single dimensional scale from the catastrophizing and optimism scores (i.e., responses from these two questionnaires will be weighted and scaled to create a single-dimensional construct)

To determine the interaction among the factors of interest, and to accommodate the many repeated measures within each participant, we will utilize Generalized Estimating Equations. In our experience, the pupil response to painful stimuli is well modeled by a normal distribution with an identity link and an AR1 repeated measures covariance structure. To examine our hypotheses, we will model percent pupil change (the DV) using fixed effects for stimulus temperature, catastrophizing-optimism score (i.e., cognitive-affective state), and pre-stimulus baseline pupil diameter (i.e., LC activity). The association between cognitive-affective state and pain reporting will first be examined, and in a later block the moderating effect of baseline pupil size will be entered.

The goal of this feasibility study is to estimate the effect size of drugs on pupil diameter and the strength of interaction between pupil diameter and the relationship between cognitive-affective state.

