Expected results. We anticipate, based on preliminary data, that pain reporting will be weakly correlated with cognitive-affective state and that resting pupil diameter as a reporter of LC gain will interact with this correlation or tendency to apply cognitive style to pain reporting. We anticipate overall reduced pain reporting after placebo (placebo effect) and that the magnitude of this reduction and that of negative of pain will be inversely related to location on the optimism-catastrophizing continuum (i.e., greater placebo effect, greater effect of negative expectations of pain, and lesser effect of positive expectations of pain in strong optimists). After gabapentin or modafinil we anticipate that resting pupil diameter will be greater (i.e. greater tonic LC activity) than placebo. According to the gain concept, the effect of gabapentin on pain reporting across conditions should depend on cognitive-affective state, with overall reductions in pain reporting in strong optimists and amplification of pain in strong catastrophizers. The study is not powered to definitively show the effects of these drugs on either pupil diameter or its relationship to pain reporting as a function of optimism-catastrophizing. Rather, it is to provide feasibility, effect size, and variability data to support the choice of drug and power analysis for the eventual controlled study.

References

1. Alexander, JK, et al. Beta-adrenergic modulation of cognitive flexibility during stress. *J Cogn Neurosci* 2007;19:468-478.
2. Astafiev, SV, et al. Comment on "Modafinil shifts human locus coeruleus to low-tonic, high-phasic activity during functional MRI" and "Homeostatic sleep pressure and responses to sustained attention in the suprachiasmatic area". *Science* 2010;328:309-
3. Chapman, CR, et al. Phasic pupil dilation response to noxious stimulation in normal volunteers: relationship to brain evoked potentials and pain report. *Psychophysiology* 1999;36:44-52.
5. Geng, JJ, et al. A match made by modafinil: probability matching in choice decisions and spatial attention. *J Cogn Neurosci* 2013;25:657-669.
6. George, SA, et al. Altered locus coeruleus-norepinephrine function following single prolonged stress. *Eur J Neurosci* 2013;37:901-909.

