A Feasibility Study: Understanding and Altering Pain Expectations in Subjects With  
Osteoarthritis of the Knee or Hip  
Statistical Analyses Plan

NCT02155257

11/02/2018

To address the two primary hypotheses, linear mixed effects models will be employed. For each model, subject will be specified as a random effect to account for the repeated measures within individuals. To examine the impact of drug (i.e., placebo, gabapentin, modafanil) on tonic pupil diameter, pupil diameter will be regressed on fixed effects for drug, time (i.e., pre-drug vs post-drug), and a drug x time interaction. A group x time integration would be interpreted as evidence supporting the hypothesis that drug differentially impacted baseline pupil over time.

To examine the impact of tonic pupil diameter on the relationship between cognitive style (i.e., catastrophizing-optimism dimension) and pain reporting, VAS scores will be regressed on fixed effects for catastrophizing-optimism, tonic pupil diameter, and the interaction between catastrophizing-optimism x pupil diameter. A statistically significant interaction would be interpreted as evidence that tonic pupil diameter moderated the relationship between cognitive style and pain reporting. Where appropriate, all analyses are two-tailed with statistical significance interpreted at  $p < 0.05$ . The analyses will be conducted using R 3.4 and R Studio.

The sample size was based on estimating the feasibility of the protocol and on establishing effect size estimates. No formal statistical power calculations were conducted.

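### The SAP's only rule for drug is a non-directional group-by-time interaction, which cannot by itself support hypothesis 1 or the choice between gabapentin and modafinil

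*SAP*

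**What the plan says.** The first paragraph of the SAP (unnumbered) presents its mixed models as addressing the two primary hypotheses. The model for the drug question has three arms and two times: "pupil diameter will be regressed on fixed effects for drug, time (i.e., pre-drug vs post-drug), and a drug x time interaction". One sentence then tells the analyst how to read it: "A group x time integration would be interpreted as evidence supporting the hypothesis that drug differentially impacted baseline pupil over time" (*integration* is evidently a slip for interaction). The second paragraph adds that, where appropriate, "all analyses are two-tailed with statistical significance interpreted at" 0.05. The SAP names no reference arm, drug-versus-placebo contrast, direction, interval or multiplicity rule.

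The Protocol is more specific in four places:
- Study Design, hypothesis 1: "Gabapentin and modafinil will increase resting pupil diameter with a moderate effect size in patients with osteoarthritis".
- Expected results, which gives the comparator: "After gabapentin or modafinil we anticipate that resting pupil diameter will be greater (i.e. greater tonic LC activity) than placebo".
- Background, on gabapentin and modafinil, which gives the decision: "Should it fail to demonstrate a reasonable effect size to dilate the pupil, we will revise the NIH application to study modafinil rather than gabapentin".
- Data analysis, which gives the purpose: "The goal of this feasibility study is to estimate the effect size of drugs on pupil diameter".

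**The concern.** The Protocol asks a directional question about each drug against placebo. The SAP's rule answers a different one: whether the three arms changed differently in any way at all. A significant joint interaction can arise because both drugs dilate the pupil, because both constrict it, because only one drug acts, or because the two act in opposite directions. The rule gives the same answer in every case.

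The drug for the later controlled study depends on this. The sponsor needs to know whether gabapentin dilates the pupil, and by how much. If modafinil alone acted, the interaction could be significant and the rule met, with nothing said about gabapentin. Leaving the contrasts unnamed also leaves the choice of comparison open until the data have been seen.

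**Working it through.** The documents state no power figure, so there is none to reproduce. The SAP says that no power calculation was made.

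**Inputs from the documents.** Three drug levels and two times (SAP, first paragraph). 30 subjects, 10 per group (Protocol, Study Design). Two-sided 0.05 (SAP, second paragraph).

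**Assumptions.** The documents give no SD and no numeric effect. Effects are therefore expressed in SD of pre-to-post change, with 0.5 standing for a moderate effect and a range up to 1.0. Each subject contributes one change score, and dropout is zero.

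**Degrees of freedom.** Interaction: (3 − 1) × (2 − 1) = 2. Residual, on one change score per subject: 30 − 3 = 27. The critical value of F(2, 27) at 0.05 is 3.354.

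**Joint test.** The noncentrality is λ = 10 × Σ(μ − mean μ)². Means are ordered placebo, gabapentin, modafinil. For (0, +0.5, +0.5) the mean is 0.333 and λ = 10 × (0.1111 + 0.0278 + 0.0278) = 1.667. Power follows from the noncentral F.

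| True pattern (SD of change) | λ | Power of joint test |
|---|---|---|
| both dilate (0, +0.5, +0.5) | 1.667 | 17.8% |
| both constrict (0, −0.5, −0.5) | 1.667 | 17.8% |
| gabapentin dilates, modafinil inert (0, +0.5, 0) | 1.667 | 17.8% |
| modafinil dilates, gabapentin inert (0, 0, +0.5) | 1.667 | 17.8% |
| both dilate (0, +1, +1) | 6.667 | 58.1% |
| both constrict (0, −1, −1) | 6.667 | 58.1% |

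Reversing every sign leaves λ unchanged, and so does exchanging the two drugs. The equalities therefore hold at any effect size; only the percentages depend on the assumed values.

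**What a significant joint result can conceal.** In 200,000 simulated trials per pattern:
- Under (0, −0.5, −0.5), both drugs were estimated below placebo in 93% of the significant results, and neither drug was significantly above placebo in 99%.
- Under (0, 0, +1), gabapentin was estimated below placebo in 50% of the significant results.

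**Two contrasts instead.** For each drug minus placebo in change, the standard error is √(2/10) = 0.447 SD on 27 df.
- The 95% CI half-width is 2.052 × 0.447 = 0.92 SD.
- At a true effect of 0.5, the noncentrality is 0.5/0.447 = 1.118. The chance of significance in the dilation direction is 18.9%, and in the wrong direction 0.1%.
- At 0.8 and 1.0, the chance of significance in the dilation direction is 40.7% and 57.8%.
- With Bonferroni (0.025 each), the chance at 0.5 falls from 18.9% to 12.0%.
- Unadjusted, two independent tests would have a familywise error of 1 − 0.95² = 9.75%. These two share the placebo arm, so the true figure is somewhat lower.

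**The case against.** Read alone, the SAP sentence is coherent. Its stated hypothesis is only that the drugs acted differently, and an interaction is valid evidence for that. The SAP does not call its test a 2-df joint test. A regression with placebo as reference gives two signed interaction coefficients, which are exactly the drug-versus-placebo differences in change. The sponsor's own criterion for gabapentin is directional, so constriction could not pass it. The Protocol also says that the study is not powered to show drug effects definitively.

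Most of this stands, and it places the fault in the interpretation rule rather than the model. It does not remove the mismatch. The SAP presents its models as addressing the primary hypotheses, the Protocol's hypothesis 1 is directional, and no rule in the SAP leads from the fitted model to that hypothesis or to the choice of drug.

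A reader might go further and infer three things that the documents do not support:
- *That the plan produces no effect size, or that a non-significant result leaves nothing for planning.* The coefficients and variances exist whatever the p-value, and both the Protocol (Data analysis, Expected results) and the SAP name effect-size estimation as an aim.
- *That the rule is met more often when the hypothesis is false.* Power is 39.9% for (0, −0.8, 0) and 45.8% for (0, +0.5, −0.5), against 17.8% for (0, +0.5, +0.5), but these patterns have larger effects or a wider spread. (0, +0.8, +0.8) also gives 39.9%, (0, −0.5, 0) also gives 17.8%, and (0, +0.25, −0.25) gives 14.3%.
- *That two-sided testing is the error.* A two-sided contrast for each drug, read with its sign, answers the question.

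One limit applies to the percentages. Resting diameter is recorded before every stimulus, and the SAP models repeated measures with a random subject effect. The figures from one change score per subject are therefore illustrative. The blindness of the joint test to sign does not depend on that simplification.

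**Conclusion.** The concern holds as a mismatch between the SAP's interpretation rule and the Protocol hypothesis that it is meant to address. A significant group-by-time interaction cannot by itself support hypothesis 1 or settle the choice between the drugs, because the joint test is blind to both sign and drug. That property is exact under equal allocation. The 17.8% figure rests on the assumed 0.5 SD, on one change score per subject and on the inferred 2 df.

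The consequence is for interpretation and drug choice, not for a failed confirmatory test. Contrasts do not rescue power either: 18.9% for each drug against 17.8% for the joint test at 0.5 SD. What they gain is an answer that identifies drug and direction. The correction should be made, and it is inexpensive.

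**What to change.** Replace the interpretation sentence in the SAP's first paragraph with the following:

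1. The primary output is two pre-specified contrasts from the same mixed model: gabapentin minus placebo and modafinil minus placebo, each in pre-to-post change of tonic diameter.
2. Each is reported in mm and as a standardised effect with a 95% CI, and the SD used for standardising is named.
3. Only a positive contrast supports hypothesis 1 for that drug.
4. Either a multiplicity rule for the two contrasts is stated, or both are declared to be for estimation only.
5. The joint interaction test is kept as descriptive.

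The contrasts should use change, not post-drug diameter alone, because change is what the interaction in the existing model estimates and it keeps the pre-drug measurement.

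The cost is SAP wording; no new data, subjects or model are needed. If multiplicity is adjusted, the threshold for each drug is stricter (with Bonferroni, 12.0% instead of 18.9% power at 0.5 SD). The intervals will be wide: an estimate of 0.5 SD would run from about −0.42 to 1.42 SD, and the later power analysis should carry that uncertainty.

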In this ongoing study we have examined pupil responses to phasic noxious heat stimuli to date in 19 normal volunteers and 4 subjects with migraine (but not in the presence of a headache). Studies were performed in a room with constant, low ambient light so that both constriction and dilation of the pupil could be observed. Pupil diameter was continuously monitored by an infrared camera (Eye-Trac™ system; Applied Science Laboratories) with the subject's chin resting on a chin rest and gaze on a fixed object presented on a monitor. A 4 cm² Peltier-controlled thermode was placed on the calf, with temperature maintained at 35°C and 5 sec stimuli at various temperatures applied every 30 sec. Subjects reported pain intensity with a visual analog scale (VAS) from 0 (no pain) to 100 (worst pain imaginable). Increasing probe temperature to 50°C resulted in pain report and pupil dilation, the former with a longer lag (Figure 2, typical response). As previously described with other stimuli (Chapman, 1999; Oka, 2007), there was a direct relationship between pupil dilation and noxious heat temperature as well as VAS pain intensity and unpleasantness.

We next examined the relationship between pupil response and pain report as a function of affective distress. We estimated affective distress as the sum of scores to the pain catastrophizing scale, the CSED depression scale, the state trait anxiety inventory, and the pain anxiety symptom scale and linearly regressed this on pain report. The residual from the regression line for each individual was related to baseline pupil diameter as a measure of tonic LC activity. Despite there being a very small range of affective distress in this largely normal population, the residual (tendency to adhere to cognitive-affective state in pain reporting) was significantly related to baseline pupil diameter (Figure 3).

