Expectations alter pain experience. We are also manipulating expectations in this study of healthy volunteers. Pain stimuli are first presented as a random series without cues, then as a series preceded by 6 sec with an auditory cue to indicate whether the stimulus would be mildly (47°C) or moderately (50°C) painful, then as a series with 20% of the cues incorrect. So far we have observed a mild, but highly significant reduction in pain from random to cued condition, consistent with a recent report on the role of uncertainty in pain reporting (Yoshida, 2013). During miscuing, there was a greater effect of negative expectations (expect less pain) than positive ones (expect more pain), as previously reported (Koyama, 2005). In the proposed

[figure not shown]

Figure 2: Time course of heat stimulus and of VAS and pupil responses

[figure not shown]

Figure 3: Relationship between resting pupil diameter and pain reporting by affective distress

study we gather feasibility data in a clinical population (patients with moderate osteoarthritis of the hip or knee) to test whether we can manipulate expectations on pain in this population.

Gabapentin and modafinil to increase LC activity and gain. In animals and humans, the alertness enhancing drug, modafinil (Provigil™) increases tonic LC activity and increases pupil diameter. Although large doses of this drug (800 mg) can increase blood pressure and heart rate, this has not been observed in these studies of over 100 people who received 200 mg (Hou, 2005; Nikolaou, 2008; Minzenberg, 2008; Schmaal, 2013; Geng, 2013). For this reason, we will examine the effects of modafinil, 200 mg, on pupil diameter and its effect to alter pain reporting as a function of baseline state by increasing gain.

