Catastrophizing-Optimism continuum assessment. Prior to the initiation of experimental procedures, each participant will be administered the battery of questionnaires Table 1. From these questionnaires, we will place each participant on a dimensional continuum that describes their general cognitive style. We will use multidimensional scaling (MDS) to force catastrophizing and optimism as 2 ends of this continuum (Figure 4). These two constructs

describe cognitive styles that are strongly inversely associated with each other; MDS will provide the optimal weights to best order individuals on this latent scale. Studies have examined the interplay of these constructs with other psychological concepts such as acceptance, pain-related disability and psychosocial adjustment and have found that both are reliably associated with the positive and negative aspects of the adjustment to pain.

Study procedures: A total of 30 subjects with moderate average daily pain from osteoarthritis of the knee or hip or subjects with no pain will be recruited and will come to the clinical research unit at Wake Forest. Informed consent will be confirmed and they will complete the questionnaires. We will take a verbal medical and medication history and obtain blood pressure and heart rate measurements. Verbal pain intensity report (0-10 from no pain to worst pain imaginable) will be obtained from 5 sec heat stimuli, separated by 30 sec, delivered to a nonpainful area of skin on the arm as described in preliminary data. During pain testing, study subjects will sit in a comfortable chair in a low-ambient light room with their head positioned on a chinrest for continuous recording of pupil diameter using a near infrared recording system as described in preliminary data. Pupil diameter and probe temperature will be passed through an analog to digital converter and acquired at 60 Hz for subsequent analysis.

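### The SAP's pain-moderation model omits stimulus temperature and cue and does not say which periods enter: this can cost precision and, if periods are pooled, can bias the interaction

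*SAP*

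**What the plan says.** The SAP's pain model has three fixed effects: "VAS scores will be regressed on fixed effects for catastrophizing-optimism, tonic pupil diameter, and the interaction between catastrophizing-optimism x pupil diameter". In both primary models "subject will be specified as a random effect to account for the repeated measures within individuals". Drug and time appear only in the other primary model, where "pupil diameter will be regressed on fixed effects for drug, time (i.e., pre-drug vs post-drug), and a drug x time interaction". The pain model is to be read as follows: "A statistically significant interaction would be interpreted as evidence that tonic pupil diameter moderated the relationship between cognitive style and pain reporting".

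Under Study procedures the protocol takes a pain score after every heat stimulus, at 47 or 50 °C. Before drug there are two uncued and two cued sequences of five, so 20 ratings. After drug both paradigms are again given twice, followed by a sequence containing miscues. Only the training sequence is excluded from analysis. The scale is described as "Verbal pain intensity report (0-10 from no pain to worst pain imaginable"; the SAP calls it VAS.

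The protocol says of cueing in its healthy-volunteer work: "So far we have observed a mild, but highly significant reduction in pain from random to cued condition". Its Data analysis section includes stimulus temperature in a model, but the outcome there is pupil change, not pain. The same section defines a local resting diameter from the 500 msec before each stimulus.

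The period is left open. The preliminary analysis, done without drug, fits a pre-drug model: "The residual from the regression line for each individual was related to baseline pupil diameter as a measure of tonic LC activity". The stated reason for studying modafinil, "its effect to alter pain reporting as a function of baseline state by increasing gain", fits a model that uses post-drug ratings as well.

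**The concern.** Temperature and cue are known for every rating and are expected to move pain. Left out, their variation goes into the residual, which can blur the one coefficient that answers primary outcome 2.

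The unstated period raises a separate issue. With pooled ratings, part of the within-subject variation in pupil is the shift caused by the drug. Anything else that changes at the same time, in the same people, and differs by cognitive style can then be credited to the pupil.

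The Data analysis section makes the strength of this interaction a goal of the study, and Expected results says the data will support the power analysis of the next trial. An imprecise or biased estimate therefore matters more here than the p-value.

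**Working it through.** The SAP did no power calculation, so there is no planned figure to reproduce.

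**Inputs from the documents:** 30 subjects, 10 per arm; 20 pre-drug ratings; 20 post-drug ratings if those sequences also have five stimuli (miscue sequence left out, as its length is not given).

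**Inputs assumed:** pain on the 0-10 scale with residual SD 1 and subject SD 1.5; temperature effect t = 2 points; cue effect c = -0.5; half of ratings at each temperature and half cued; style in SD units, higher meaning more optimistic; pupil between-subject SD 1 and stimulus-to-stimulus SD w = 0.5 (or 0.3); pupil shift s = 0.5 or 0.8 in both active arms.

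**Step 1. Precision, per-stimulus pupil.** Without the two terms the residual variance is 1 + t²/4 + c²/4:

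- t = 1: 1 + 0.25 + 0.0625 = 1.3125; SE cut 1 - 1/√1.3125 = 13%
- t = 2: 1 + 1 + 0.0625 = 2.0625; SE cut 1 - 1/√2.0625 = 30%
- t = 3: 1 + 2.25 + 0.0625 = 3.3125; SE cut 1 - 1/√3.3125 = 45%

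This treats all information as within-subject, so it slightly overstates the gain. Simulated trials at t = 2 give:

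| Ratings used | w | SE without | SE with | Cut |
|---|---|---|---|---|
| Pre-drug | 0.5 | 0.117 | 0.084 | 28% |
| Pooled | 0.5 | 0.078 | 0.056 | 28% |
| Pre-drug | 0.3 | 0.174 | 0.132 | 24% |
| Pooled | 0.3 | 0.112 | 0.081 | 28% |

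An independent run at w = 0.5 gave 0.118 to 0.085 and 0.078 to 0.055, cuts of 28% and 29%. For a true interaction of -0.10, power rises from 25% to 44% pooled (shift 0.5) and from 13% to 22% pre-drug.

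**Step 2. Precision, one pupil value per subject, one period.** The interaction is now estimated between subjects, and temperature and cue are close to balanced within each subject. The simulated SE is 0.331 with or without the two terms. If temperature is drawn fully at random, the variance of a subject mean is 2.25 + 2/20 = 2.35 without temperature and 2.25 + 1/20 = 2.30 with it, a cut of 1 - √(2.30/2.35) = 1%. Analysing subject-by-period mean scores likewise loses little.

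**Step 3. Pooled periods, true interaction zero.** Suppose post-dose pain falls by a further d points per SD of style, by a route other than the pupil. Let f be the fraction of all subjects who have both this change and the pupil shift. The within-subject slope that falls on style x pupil is approximately

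-(f·s·d/4) / (w² + (2/3)·s²/4).

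With d = 0.3, s = 0.5, w = 0.5 the denominator is 0.25 + 0.0417 = 0.2917:

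- every arm changes, f = 2/3: -0.025/0.2917 = -0.086 (simulated -0.08)
- gabapentin arm only, f = 1/3: -0.0125/0.2917 = -0.043 (simulated -0.04)
- placebo arm only, f = 0: 0 (simulated about 0)
- uniform change, d = 0: 0

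The SE is about 0.08. Over d = 0.2 to 0.5 and s = 0.5 to 0.8, false positives at a nominal 5% are 6 to 26% (gabapentin only) and 10 to 67% (every arm). They stay near 5% for a placebo-only change, and at 5.5 to 5.6% for pre-drug ratings only. A uniform change gave 5.8% in a separate simulation with different assumed variances.

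**Step 4. What the remedies do if periods are pooled.** Temperature and cue alone leave the bias in place and, by shrinking the SE, make it significant more often (9 to 43% and 18 to 88%). Adding a subject-by-period random effect brings false positives to 6 to 13%, or up to 30% with w = 0.3. A model with style x period x arm and all lower-order terms gives 5.5 to 5.8%.

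**The case against.** The SAP may intend one baseline pupil value per person, as in the protocol's preliminary analysis. Temperature and cue then hardly matter. This stands: a reader might infer that the omission costs precision however the model is fitted, and Step 2 shows that it does not. The protocol's per-stimulus definition favours the reading on which there is a loss, but the SAP does not say so.

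The bias needs four things together: pooled periods, a style-dependent change, a route that bypasses the pupil, and a wider pupil in the same subjects. The only style-related change that Expected results states apart from gain is the placebo response after placebo, which produces no bias. It credits gabapentin's style-dependent effect to gain; on that mechanism the interaction is signal. This also stands. A reader might infer that a significant interaction would be an artefact, or that the protocol predicts the bias; the documents support neither. The case in which every arm changes is an inference of this review.

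The protocol says the study is not powered for definitive conclusions. That lowers the weight of the p-value but does not protect the effect-size estimate, which is what the study is meant to deliver.

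**Conclusion.** The omission of temperature and cue, and the silence on periods and on the level of tonic pupil, can be read directly from the SAP. With per-stimulus pupil and a 2-point temperature effect, the two terms would cut the interaction's SE by roughly 24 to 29%; the range is about 13 to 45% for effects of 1 to 3 points. With one pupil value per subject in one period the gain is essentially nil.

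The bias is conditional on pooling and on the other three conditions. Under the middle scenario it is about half to one SE, in the direction that the gain hypothesis predicts. The direction and the conditions follow from the model's structure. Every magnitude rests on assumed variances and effects, because the documents give none. This should be fixed, with medium confidence; it does not make the planned analysis invalid.

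**What to change.** In the SAP:

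1. Add stimulus temperature and cue condition as fixed effects in the pain model, with the miscued sequence as a third cue level if it is analysed.
2. Define tonic pupil as the per-stimulus local resting diameter in the protocol's Data analysis section, or state another level, and state which periods enter.
3. If periods are pooled, add a subject-by-period random effect. Report beside the primary result a sensitivity model with period, arm and their products with cognitive style, and the pre-drug-only estimate. If these disagree, describe the pooled interaction as moderation only with caution. No numerical agreement threshold is needed.

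Cost: wording, two or three fixed effects and, if pooled, one variance component; no new data. The random effect costs little power in the simulations (51.2% to 50.5% at shift 0.8; 32.5% to 30.9% with pupil SD 0.3), but it reduces the bias without removing it. The sensitivity model discards drug-induced pupil variation and so has less power: 37% against 44% at shift 0.5 and 51% at 0.8, and 16% against 33% at shift 0.8 with pupil SD 0.3. That is why it should sit beside the primary model and not replace it.
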